Study Title: Efficacy and Cost-effectiveness of Intra-Articular Ketorolac Injection for Knee Osteoarthritis: A Randomized, Controlled, Double-Blinded Study

NCT: 03694821

Last IRB Approval Date: 6/25/2019

Study Protocol

1. Title of the Study

Efficacy and Cost-effectiveness of Intra-Articular Ketorolac Injection for Knee Osteoarthritis: A Randomized, Controlled, Double-Blinded Study

Principal Investigator's Name and Contact Information

[name]

Assistant Professor, Department of Orthopaedic Surgery

University of Connecticut Health Center

[name]

Study Personnel

[name] PT, DPT, MSCTR (Statistician)

[name], BS (Study Coordinator)

[name], MS (Study Coordinator)

2. **Background**

Osteoarthritis (OA) of the knee is a common debilitating disorder with tremendous socioeconomic impact.^{1,2} The estimated financial burden of OA, including healthcare expenses and loss of productivity, is in excess of \$140 billion annually.^{2,3} Nonoperative management emphasizing rehabilitation, weight loss, and nonsteroidal anti-inflammatory drugs (NSAIDs) is currently the first line treatment for symptomatic OA of the knee.⁴ Other interventions, such as intra-articular injections with either corticosteroids or viscosupplements, remain controversial with mixed results in the literature.⁵⁻⁸

There is limited information about NSAIDs injection for the treatment of knee OA. Given that OA involves inflammatory processes leading to cartilage degradation and pain,⁹ NSAIDs injection represents a promising modality allowing for higher local tissue concentration and potentially providing potent anti-inflammatory and analgesic effects. In the US, ketorolac is the only NSAID available in injectable form. The advantages of ketorolac injection are multifold: 1) it is a relatively inexpensive medication; 2) there is strong evidence to support NSAIDs use, administered orally or topically, in the treatment of knee OA;¹⁰ 3) injection may be associated with less risk of systemic side effects¹¹ especially in patients who cannot tolerate oral NSAIDs; 4) ketorolac can potentially avoid the complications associated with corticosteroids, such as joint infection, cartilage breakdown, and loss of cartilage elasticity^{9,12,13}; and 5) ketorolac eliminates the risk of acute inflammatory reactions or need for serial clinic visits associated with viscosupplementation, which is ranked as the second highest OA-related healthcare expenditure.¹⁴

To date, there is a single published study on ketorolac vs. corticosteroid injection for knee OA, which showed similar pain relief but cost savings of 143% when using ketorolac.¹⁵ However, that study had only 35 patients with no power analysis. In addition, patients with no to minimal joint space narrowing or those with concomitant use of the study medications orally were not excluded. Most importantly, the corticosteroid used in that study has been voluntarily discontinued in the US market.

3. **Hypothesis, aims and objectives:**

- *Hypothesis:* Ketorolac injection is a cost-effective adjunct in the nonoperative treatment of knee osteoarthritis (OA) compared to steroids and viscosupplementation.
- *Aims/objectives:* The objective of this randomized, controlled, double-blinded, prospective study is to assess the efficacy and cost-effectiveness of knee injection with ketorolac in the nonsurgical

management of symptomatic OA compared to injections with corticosteroids and viscosupplements.

4. Study Design & Procedures:

Study Design: A prospective, randomized, controlled, double-blind trial.

- *Screening Procedures and who will perform them:*

Patients will be screened for eligibility when they present to the office for evaluation of knee pain. Screening will consist of a review of patients' medical history, physical exam, and X-rays which are routinely performed with or without being considered for a research study. If during the visit, a patient is interested in knee injections for symptomatic relief as part of conservative management, the patient will be informed of the possibility of participating in the research study and asked if there is interest in learning more. If the patient is interested, the investigators will make a note to the chart and let the patient know that the Study Coordinator (SC) will come by to present the details of the study, and inform the SC of the patient's interest. The SC will approach the patient at the end of the visit to provide an overview of the study and ask for verbal permission to review the patients chart to confirm eligibility. If found eligible, the SC will then proceed with a full consent process. Alternatively, if the patient prefers, a separate visit may be scheduled to conduct the consent process. Only study members will be allowed to obtain consent for study participation.

- *Randomization:*

Patients will be allocated to one of three groups using a web-based randomization by the SC: ketorolac, methylprednisolone, or hyaluronic acid. Group assignments will be concealed in opaque sealed envelopes with a numerical code of consecutive numbers reflecting patient enrollment. Envelopes will be stored in a secure, locked desk in the UConn orthopaedic research office and only to be opened once a patient has been determined to be eligible for study inclusion and provided informed consent.

Once informed consent is obtained, a licensed provider who is not part of the data collection (to maintain blindness) will prepare and inject the study drug. The patient will receive one of three options: 2cc of ketorolac tromethamine (15mg/cc) in 5cc of 0.5% ropivacaine hydrochloride without epinephrine, 2 cc of methylprednisolone acetate (40mg/cc) in 5cc of 0.5% ropivacaine hydrochloride without epinephrine, or Hylan G-F 20 (Synvisc-One) injection. In the US, methylprednisolone acetate is the most commonly used intra-articular steroid.¹⁷

- *Intervention: Each patient will receive one of the following interventions:*

- 1) 2cc of ketorolac *tromethamine* (15mg/cc) in 5cc of 0.5% *ropivacaine hydrochloride* without epinephrine; OR
- 2) 2 cc of methylprednisolone acetate (40mg/cc) in 5cc of 0.5% *ropivacaine hydrochloride* without epinephrine; OR
- 3) Hylan G-F 20 (*Synvisc-One*) or available hyaluronic acid.

- *Blinding:*

Both the patient and the investigators will be blinded to the treatment used until after final follow-up. Patients will not be told which drug they received. The investigators will be blinded too because the injections will be performed by a licensed provider who is not part of the data collection. Only the study coordinator will know which drug was administered and will compile the data until the study is completed.

- *Data collection:*

Patients will be asked to complete VAS, WOMAC, Oxford Knee questionnaire and Koos, Jr. Knee Survey prior to knee injection. Follow-up length is 6 months.

▪ *Sample Size and Justification:*

A sample size calculation was performed to determine the adequate number of patients needed per group. A difference of 2 points in pain on a visual analog scale (VAS) was selected as the threshold for a meaningful between group difference. A standard deviation of 2.0 points was assumed based on previous research comparing steroid to viscosupplementation for osteoarthritis of the knee. A sample size of 20 patients per group will provide 80% power (β of 0.20) to detect a 2-point difference at an α level of 0.05 among the 3 treatment groups in an omnibus one-way ANOVA. To account for post hoc comparisons, a second calculation was carried out using a Bonferroni correction. A sample size of 25 patients per group will provide 81% power (β of 0.20) to detect a 2-point difference between each group in post hoc testing. To verify the sample size calculation, a Monte Carlo program was used to simulate 1,000 ANOVAs using these estimates with a sample size of 25 per group. This analysis resulted in greater than 90% power for the omnibus one-way ANOVA and greater than 80% for post hoc testing of between group means.

Explain on what basis it is reasonable to assume that sample size will be obtained:

Knee OA is a very common musculoskeletal condition, accounting for a significant proportion of patients presenting to orthopaedic providers.

Subject Characteristics and Justifications:

- Age: 18 years or older
- Ethnicity: No restrictions.
- Gender: No restrictions.
- Vulnerable Populations: None will be included.

Inclusion Criteria:

Patients over the age of 18 who present with 1) symptomatic knee OA and radiographic evidence of joint space narrowing and 2) are interested in knee injections for pain relief.

Exclusion Criteria:

- Patients interested in bilateral knee injections,
- Prior injections into the same knee within the past 3 months,
- Pregnant and/or lactating women,
- Inflammatory joint disease including rheumatoid or psoriatic arthritis,
- Concurrent use of anti-rheumatic drugs,
- Allergy or hypersensitivity to the study medications,
- Patients on an active pain management contract,
- Inability to make own decisions regarding the informed consent,
- Inability to read and/or understand English,
- Patients who are unable to return for follow-up or be reached by phone
- Patients with insurance that requires pre-certification for any of the study drugs.

Describe length of subject's participation in the study including number of visits, frequency of visits and length of visits:

Patients will be in the study for 6 months. This time period will encompass their initial visit at which point they will be enrolled in the study and receive the injection as well their follow up visits. Patients will be asked to return at 3 and 6 months for evaluation and data collection. These visits are considered routine practice at our institution. Patients may also be contacted via telephone or email for follow-up if necessary. Participation will be voluntary with no financial compensation.

Methods of Data Collection and Types of Data to be Collected:

Data will consist of demographic information (age, gender, body mass index, comorbidities, etc.), as well as previous treatment modalities. The primary outcome is a visual analogue scale (VAS) for pain. Secondary measures will include the Western Ontario and McMaster Universities Osteoarthritis Index (WOMAC), length of pain relief, patient satisfaction, non-routine visits due to inadequate pain relief or complications, and cost of intervention.

Methods of Data Analysis:

Results for continuous variables will be described using means, standard deviations, medians, and/or interquartile ranges. Categorical variables will be described using counts and percentages. Numerical variables will be compared between groups using Wilcoxon's rank-sum test or Welch's two sample t-test. Categorical variables will be compared between groups using Pearson's chi-squared test or Fisher's exact test. All analyses will be done using R software (R version 3.2.3 (2015-12-10), Vienna, Austria) assuming a 5% level of significance.

5. Timetable:

Expected start date: 1/1/18

General Time Table: 1 year

Expected Completion Date: 7/31/20

6. Budget/Resources:

We will be applying for Orthopaedic Research and Education Foundation Grant during the IRB review.

7. Dissemination:

We plan to disseminate the results of our research in the form of peer reviewed publication and presentation at specialty meetings.

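### The plan tests only for differences and has no rule for reading a non-significant pain result, although similar pain relief at lower cost is a result that would support its hypothesis

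*Combined protocol and SAP*

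**What the plan says.** Section 3 frames a comparative question. The hypothesis reads "Ketorolac injection is a cost-effective adjunct in the nonoperative treatment of knee osteoarthritis (OA) compared to steroids and viscosupplementation". The objective is to "assess the efficacy and cost-effectiveness of knee injection with ketorolac in the nonsurgical"; after a line break in the text, the same sentence goes on to name the comparators: "management of symptomatic OA compared to injections with corticosteroids and viscosupplements". It does not say whether ketorolac is expected to be superior, non-inferior or equivalent on pain.

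The Randomization paragraph gives three active arms: "Patients will be allocated to one of three groups using a web-based randomization by the SC: ketorolac, methylprednisolone, or hyaluronic acid".

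Sample Size and Justification fixes the effect of interest: "A difference of 2 points in pain on a visual analog scale (VAS) was selected as the threshold for a meaningful between group difference". It assumes an SD of 2.0 and arrives at 25 per group for Bonferroni-corrected post hoc comparisons. The 2 points serve only as a difference to detect.

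Methods of Data Analysis lists descriptive summaries, Wilcoxon or Welch tests for numerical variables, and chi-squared or Fisher tests for categorical ones, all at 5%. It mentions no confidence interval, margin or rule for interpreting a non-significant result, and it does not repeat the ANOVA or the Bonferroni correction. Follow-up visits are at 3 and 6 months, and neither is named as primary for the VAS.

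The Background summarises the one earlier ketorolac-steroid trial as one "which showed similar pain relief but cost savings of 143% when using ketorolac", and notes that it had 35 patients and no power analysis.

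**The concern.** The Background puts ketorolac's low price first among its advantages, and the hypothesis is about cost-effectiveness. Two kinds of pain result could support it: ketorolac relieves pain better, or it relieves pain about as well and costs less. The planned tests address only the first. For the second, the analyst would have a p-value above 0.05 and nothing in the plan that says what it means.

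A p-value above 0.05 is compatible with no difference and also with a real disadvantage that the sample could not resolve. If it were carried into the cost-effectiveness argument as similar relief, the trial would repeat the inference that the Background reports from the earlier study, whose size and lack of a power analysis the protocol itself criticises. A threshold chosen after the data are seen would carry little weight, so the reading rule has to be written beforehand.

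**Working it through.** **Inputs.** SD 2.0, meaningful difference 2 points, 25 per group and alpha 0.05, all from Sample Size and Justification. Assumptions where the plan is silent: two-sided tests, Bonferroni over three pairs (0.05/3 = 0.0167), higher VAS meaning more pain, and no dropout.

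**The plan's own figures.** Noncentral F with group means 0, 1, 2 and 20 per group gives omnibus power of 79.3%, which matches the stated 80%. For the post hoc comparison at 25 per group and alpha 0.05/3, the noncentral t gives 85.0% and a Wilcoxon simulation 82.3%, against the stated 81%. The t formula reaches 81% at 23 per group. The stated sizes are close enough to use.

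**Precision.** SE = 2.0 × √(2/25) = 0.566.
- 95% half-width: t(48) × SE = 2.011 × 0.566 = 1.14 points.
- Bonferroni half-width: 2.480 × 0.566 = 1.40 points.

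**Chance of a non-significant pairwise test.** This is 1 minus power from the noncentral t, df 48, noncentrality = true deficit / 0.566.

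| True ketorolac deficit | Alpha 0.05 | Alpha 0.05/3 |
|---|---|---|
| 0 | 95% | 98% |
| 0.5 | 86% | 94% |
| 1.0 | 59% | 75% |
| 1.5 | 26% | 43% |
| 2.0 | 7% | 15% |

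**What a non-significant result leaves open (simulation, 95% intervals).** With a true 1-point deficit, 96% of non-significant results have an interval reaching a deficit of 1 point or more, 77% one of 1.5 or more, and 33% one of 2 or more. With no true difference, the figures are 59%, 25% and 5%. The test result alone does not tell these cases apart; the interval does.

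**Reading the interval against 2 points.** At the expected half-width, the interval excludes a 2-point disadvantage when the observed deficit is below 2 − 1.14 = 0.86, and the test is significant when it exceeds 1.14. Between 0.86 and 1.14 the result is non-significant and a 2-point deficit remains possible. With Bonferroni that band runs from 2 − 1.40 = 0.60 to 1.40.

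If ketorolac is truly 2 points worse, the interval wrongly excludes 2 points in 0.05/2 = 2.5% of trials (0.0167/2 = 0.8% with Bonferroni). Treating non-significance as similarity would be wrong in 7% (15%).

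**What the planned size supports (noncentral t, 25 per arm).**

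| Situation | 95% interval | Bonferroni interval |
|---|---|---|
| Truly equal, interval excludes 2.0 | 93% | 85% |
| Truly equal, interval excludes 1.5 | 74% | 57% |
| Truly equal, interval excludes 1.0 | 41% | 25% |
| Ketorolac truly 1 point worse, interval excludes 2.0 | 41% | 25% |

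Adjusting only for the two ketorolac comparisons (alpha 0.025) gives 89% in the first row. Excluding 2 points against both comparators together, with unadjusted intervals, has probability 89%. The plan makes no allowance for dropout; with 20 analysed per arm, the first row becomes 87% and 74%.

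**The case against.** The objective is relative and the comparators are active, so the design fits the question. A significant advantage over either comparator would be a valid relative result. By the plan's own standard, deficits of 1 or 1.5 points are not meaningful, so missing them is no failure; at a 2-point deficit the test is non-significant only 7% of the time (15% with Bonferroni). The plan reports means and SDs, from which a reader can calculate an interval. No passage says that p > 0.05 will be read as similarity. All of this stands. It limits the point to the missing reading rule, and it means the trial is not uninformative.

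It is also fair that 2 points, a full SD, was chosen as a difference to detect. Using it as a formal non-inferiority margin would need the comparators' effect over placebo, which the documents do not give. The interval reading must therefore be worded narrowly.

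Three stronger readings are tempting, and the documents do not support them:

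- *The lack of a placebo arm is the defect.* The Background does say that steroid and viscosupplement injections "remain controversial with mixed results in the literature". But section 3 asks about ketorolac relative to those injections, and that can be answered without an inert arm. The absence limits what may be concluded; it does not contradict the objective.
- *Falls from baseline within an arm will be presented as efficacy.* The analysis section plans between-group tests and descriptive summaries, and no such claim.
- *A null result is the expected outcome.* That is a forecast. It would rest on one small ketorolac-steroid study that the protocol itself faults, and the documents describe no ketorolac-hyaluronic acid result.

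**Conclusion.** The concern holds as a gap in the analysis plan. Under the plan as written, a non-significant VAS comparison could not support the similar-relief route to the hypothesis, because nothing defines when ketorolac counts as not meaningfully worse. The planned precision is ±1.14 points (±1.40 with Bonferroni), and a true 1-point deficit would be non-significant in 59% (75%) of trials.

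Sample size is not the obstacle at the plan's own 2-point threshold: truly equal drugs would meet it in about 93% (85%) of trials. That depends on the threshold. At 1.5 or 1.0 points the unadjusted figures fall to 74% and 41%. The results rest on SD 2.0, 25 analysed per arm, two-sided tests and approximate normality.

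This is a worthwhile improvement at almost no cost. It does not show that the trial is invalid.

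**What to change.** In section 3 and Methods of Data Analysis, state that:

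1. One follow-up visit is named as the primary time point for the VAS, and at that visit each ketorolac-minus-comparator difference is reported with a multiplicity-adjusted confidence interval. The adjustment and the number of comparisons are specified.
2. Each interval is read against the plan's own 2-point meaningful difference. A non-significant test whose interval still includes a 2-point disadvantage is reported as inconclusive, never as similar.
3. An interval that excludes a 2-point disadvantage supports only the statement that ketorolac is not worse than these injections by the plan's meaningful difference. It does not show efficacy over no treatment.
4. The interval is shown whatever the conclusion.

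The cost is protocol and analysis wording; no patients, visits or procedures are added. Some results that would otherwise have been called similar become inconclusive. The threshold is also lenient: a drug truly 1 point worse would meet it in 41% of trials (25% with Bonferroni), which is why item 4 is needed. If the investigators prefer a stricter threshold, they should set and justify it before seeing data and accept the lower probabilities shown above or enlarge the trial.

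### The objective rests on two ketorolac contrasts, but the plan designates neither as primary: the sizing covers all pairs and the analysis tests unnamed pairs at an uncorrected 5%

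*Combined protocol and SAP*

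**What the plan says.** All places are in the combined protocol and SAP.

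- **Section 3, Hypothesis, aims and objectives.** The hypothesis is that "Ketorolac injection is a cost-effective adjunct in the nonoperative treatment of knee osteoarthritis (OA) compared to steroids and viscosupplementation". The objective is "to assess the efficacy and cost-effectiveness of knee injection with ketorolac in the nonsurgical" management of symptomatic OA, against corticosteroid and viscosupplement injections. That makes two contrasts, each involving ketorolac. Steroid against hyaluronic acid is not a stated question.
- **Section 4, Randomization.** "Patients will be allocated to one of three groups using a web-based randomization by the SC: ketorolac, methylprednisolone, or hyaluronic acid".
- **Section 4, Sample Size and Justification.** "A difference of 2 points in pain on a visual analog scale (VAS) was selected as the threshold for a meaningful between group difference", and "A standard deviation of 2.0 points was assumed". Twenty per group is said to give 80% power "to detect a 2-point difference at an α level of 0.05 among the 3 treatment groups in an omnibus one-way ANOVA". A second, Bonferroni-corrected calculation gives 25 per group and 81% power for post hoc differences between all the groups. The number of comparisons in the correction is not stated, and no pair is singled out.
- **Section 4, Methods of Data Collection and Types of Data to be Collected.** "The primary outcome is a visual analogue scale (VAS) for pain". Cost is a secondary measure.
- **Section 4, Methods of Data Analysis.** "Numerical variables will be compared between groups using Wilcoxon's rank-sum test or Welch's two sample t-test", at a 5% significance level. ANOVA, Bonferroni and named pairs do not appear here.

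**The concern.** The question is directed at ketorolac, while the testing plan treats the three arms symmetrically. Read with the sizing section, a share of the 5% goes to a pair that the trial does not ask about, and power on the two relevant pairs falls. Read with the analysis section, each pair is tested at 5%, and the chance of at least one false ketorolac finding is nearly double the stated level.

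Because no contrast is designated, the plan also does not say what a mixed result means. If ketorolac differs from one comparator only, the text does not say what may be claimed, and that could be settled after the data are seen.

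**Working it through.** **Inputs.** Difference 2 points, SD 2.0, 25 per group, three groups, significance level 0.05 (sample size and analysis sections). Assumptions not in the documents: two-sided tests, normal data, no dropout, and Bonferroni over three pairs where the plan gives no number.

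**1. The plan's own figures.**

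- *Omnibus test, 20 per group.* The noncentrality is n × Σ(μi − mean)² / SD². With means 0, 1, 2 it is 20 × (1 + 0 + 1) / 4 = 10. The critical F on 2 and 57 df is 3.159, and power is 79.3%, which matches the stated 80%.
- *Post hoc test, 25 per group.* The noncentrality is 2 / (2 × √(2/25)) = 3.536 on 48 df. At 0.05/3 the critical t is 2.481 and power is 85.0%, above the stated 81%. A rank-sum test, by simulation, gives 81.9%, which is close. The t-test reaches 81.2% at 23 per group. The stated sample size is therefore not too small on these inputs.

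**2. Power for one ketorolac contrast (same noncentrality, 3.536).**

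| Level per test | Critical t | Power |
|---|---|---|
| 0.05/3 (three-pair Bonferroni) | 2.481 | 85.0% |
| 0.05/2 (first Holm step, two contrasts) | 2.314 | 88.5% |
| 0.05 (uncorrected) | 2.011 | 93.4% |

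Holm rejects whenever p is below 0.025, and also when p is below 0.05 and the other contrast has p below 0.025. So 88.5% is a floor. With rank-sum tests the same comparison is 81.9% at 0.05/3 against 86.3% at 0.05/2.

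**3. Power for both contrasts, ketorolac 2 points from each comparator.** The two contrasts share the ketorolac arm, so this was simulated.

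- Three-pair Bonferroni: 75.7%.
- Holm over two contrasts: about 88%.
- Two uncorrected tests: 88.5%.

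Under Holm, at least one contrast is significant in 96.0%. By symmetry, power per contrast in this setting is (96.0 + 88.0) / 2 = 92.0%.

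**4. Any false ketorolac claim when all three means are equal.** Two independent tests at 5% would give 1 − 0.95² = 9.75%. The shared arm lowers this slightly. Simulation gives:

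- two uncorrected tests: about 9%;
- Holm over two contrasts: 4.6% to 4.8%;
- three-pair Bonferroni: 3.1%, that is, less than the ketorolac question is allowed.

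**5. A mixed result.** Suppose ketorolac equals steroid and lies 2 points from hyaluronic acid. With three-pair Bonferroni, exactly one ketorolac contrast is significant in 84% of trials. The plan does not say what that outcome supports.

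**The case against.** **All-pairs testing is a common choice in a three-arm trial, and the objective already shows which two pairs matter.** The 25 per group comes from the pairwise calculation, so both ketorolac contrasts are covered with adequate power. This stands: no shortage of patients is shown. But the objective does not allocate alpha, and the analysis section drops the correction on which the sizing relied.

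**The number of Bonferroni comparisons is not stated.** This also stands. If two were meant, power per contrast is already 88.5%, and Holm adds only the gain for both contrasts, from 80.8% to about 88%. The missing correction in the analysis section remains.

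**Holm is less powerful than the uncorrected tests in the analysis section.** True: 93.4% per contrast falls to between 88.5% and 92.0%. That is the price of bringing the false-claim rate from 9% to about 5%.

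Two stronger readings are tempting, and the documents support neither.

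- *A reader might infer that the trial can succeed on an omnibus test that shows nothing for ketorolac.* With steroid and hyaluronic acid 2 points apart and ketorolac midway, the omnibus test is significant in 88% of trials. In about 40% it is significant with neither ketorolac contrast below 0.05/3. But ANOVA appears only in the sizing text and is nowhere a success criterion. The 40% depends on three-pair Bonferroni and falls to 17% at 5% per test. Ketorolac is also only 1 point from each comparator there, half the plan's meaningful difference.
- *A reader might infer that the hypothesis requires ketorolac to be superior to both comparators on VAS.* The hypothesis is one of cost-effectiveness, and similar pain relief at lower cost could support it. The Background describes an earlier trial with that pattern. A result against one comparator only is therefore not a failure by the plan's own words; it is unclassified.

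**Conclusion.** The concern holds in a limited form. The objective has two ketorolac contrasts, and no section designates them as primary or fixes how alpha is shared between them. Naming them and using Holm raises power by at least 3.5 percentage points per contrast (88.5 − 85.0) and by about 12 points for both (88 − 76) relative to three-pair Bonferroni. Relative to two uncorrected tests, it brings false ketorolac claims from about 9% to about 5%.

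These figures rest on SD 2.0, a 2-point difference, 25 evaluable patients per group, normal data, two-sided tests and three Bonferroni comparisons. This is worth correcting before analysis, but it does not show that the sample size is inadequate, that the omnibus test decides the trial, or that superiority over both comparators is required.

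**What to change.** In Sample Size and Justification and in Methods of Data Analysis:

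1. Name ketorolac versus methylprednisolone and ketorolac versus hyaluronic acid on VAS as the two primary contrasts, tested with Holm at a two-sided family-wise 5%.
2. State that a significant contrast supports a claim of a VAS difference against that comparator only.
3. Report steroid versus hyaluronic acid as an estimate with a confidence interval.
4. Treat any omnibus ANOVA as descriptive.

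The family contains two tests only if each contrast is tied to one visit (3 or 6 months) and one test (rank-sum or Welch), so the same text should settle both.

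The cost is a few sentences, with the same 75 patients. What is lost is a confirmatory claim for steroid versus hyaluronic acid, which the objective does not ask for.

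### Three arms sized with Bonferroni pairs but analysed under a section with no multiplicity rule: a binding 5% omnibus test, then uncorrected pairs, would settle both and gain power at 25 per arm

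*Combined protocol and SAP*

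**What the plan says.** Under Sample Size and Justification (section 4), the plan sets the target and the spread: "A difference of 2 points in pain on a visual analog scale (VAS) was selected as the threshold for a meaningful between group difference", and "A standard deviation of 2.0 points was assumed based on previous research comparing steroid to viscosupplementation for osteoarthritis of the knee". Twenty patients per group are said to give 80% power "to detect a 2-point difference at an α level of 0.05 among the 3 treatment groups in an omnibus one-way ANOVA".

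The size is then raised for the pairs: "To account for post hoc comparisons, a second calculation was carried out using a Bonferroni correction". The result for these pairwise tests is given as: "A sample size of 25 patients per group will provide 81% power (β of 0.20) to detect a 2-point difference between each group in post" (quote cut short). A simulation at 25 per group is reported: "This analysis resulted in greater than 90% power for the omnibus one-way ANOVA and greater than 80% for post hoc testing of between group means". The section does not give the Bonferroni divisor, does not state the assumed means of the three arms, and does not say that pairs are tested only if the ANOVA is significant.

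Methods of Data Analysis, also in section 4, mentions neither the ANOVA nor the Bonferroni correction. It lists the Wilcoxon rank-sum test or Welch's t-test for numerical variables, at a 5% level.

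The objective in section 3 is to assess ketorolac in the nonsurgical "management of symptomatic OA compared to injections with corticosteroids and viscosupplements". Two contrasts therefore carry the question: ketorolac against steroid, and ketorolac against viscosupplement.

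**The concern.** The two sections describe different procedures, and neither is the best one available for three arms.

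The sizing procedure pays for multiplicity twice if the ANOVA is meant to come first: once through the 5% omnibus test and again through Bonferroni on the pairs. With three arms the second payment is not needed. The analysis section, read as written, pays nothing and leaves the family-wise error uncontrolled.

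At stake are a clear error rate for the primary comparison and the chance of answering both ketorolac questions from the same 75 patients (3 × 25). The plan's power figure is per pair and does not give the chance of establishing both differences.

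**Working it through.** **Inputs.** From Sample Size and Justification: difference 2 points, SD 2.0 (standardised difference 2/2.0 = 1.0), 20 or 25 per group, α 0.05. From Randomization: three arms. Assumed because not stated: equal allocation, two-sided tests, every patient analysed, and a Bonferroni divisor of 3 (0.05/3 = 0.0167), with 2 as an alternative (0.025).

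**1. The plan's own figures.** For the omnibus test the noncentrality is λ = n Σ(μᵢ − μ̄)²/σ².
- Means 0/1/2, n = 20: λ = 20 × 2/4 = 10; power 79.3%. The stated 80% reproduces.
- Means 0/1/2, n = 25: λ = 25 × 2/4 = 12.5; power 88.3%.
- Means 0/2/2, n = 25: λ = 25 × 2.667/4 = 16.7; power 95.6%. The reported figure above 90% fits this pattern and not 0/1/2.

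For one pair at 25 per group, δ = 2/(2.0 × √(2/25)) = 3.54. At α = 0.0167 two-sided, power is 85.0% (t, 48 df), 85.8% (pooled error, 72 df) or 87.3% (normal). The stated 81% does not reproduce with t-tests; it corresponds to about 22 or 23 per group. A Wilcoxon version gives 82.0%. The stated figure is therefore conservative.

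**2. Why three arms are special.** Test pairs at 5% only after a significant 5% omnibus test.
- All three means equal: any false claim must first pass the omnibus test, so the error is at most 5%.
- Two equal, one different: only one true null pair remains, tested at 5%.
- All different: no pairwise null is true.

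These cases are exhaustive, so this is a closed test. Bonferroni applied after the same omnibus test can only reject fewer pairs. The argument does not extend to four or more arms.

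**3. Family-wise error by simulation** (25 per arm, 40,000 to 400,000 trials per pattern; 60,000 for rank tests).
- Omnibus test, then uncorrected pairs: 5.0% with all means equal and about 5% with two equal.
- Uncorrected pairs with no omnibus step: 12.1% over three pairs, 8.9% over the two ketorolac contrasts.
- SDs of 1.5, 2 and 3 (illustrative): an ordinary F test first gives 5.7%; a Welch ANOVA first gives 5.0%.
- Kruskal-Wallis, then Wilcoxon: 4.9%.

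**4. Power by simulation**, ketorolac 2 points from both comparators, comparators equal, omnibus test first in every row:

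| Procedure | Per ketorolac contrast | Both jointly |
|---|---|---|
| Bonferroni, 3 pairs, pooled | 85.8% | 77.1% |
| Bonferroni, 2 pairs, pooled | 88.8% | 82.0% |
| Uncorrected pairs, pooled | 92.3% | 88.9% |
| Bonferroni, 3 pairs, Welch | 84.8% | 75.6% |
| Uncorrected pairs, Welch | 91.6% | 88.1% |

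Against three-pair Bonferroni the joint gain is 88.9 − 77.1 = 11.8 points (pooled) or 88.1 − 75.6 = 12.5 points (Welch). The per-contrast gain is 6.5 or 6.8 points. Running Bonferroni without the omnibus step leaves joint power at about 77% (pooled).

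**5. Other patterns.**
- Means 0/1/2: the 2-point pair goes from 85.5% to 87.9%, a gain of 2.4 points; the 1-point pairs go from about 25% to 41%.
- Comparators on opposite sides of ketorolac: joint power goes from 70-72% to 87%.
- Rank tests, equal comparators: joint power goes from 71.5% (Bonferroni) to 85.7% (Kruskal-Wallis first).
- Only 20 analysed per arm (illustrative), equal comparators: joint power is 61-63% with Bonferroni and 78-79% with the closed test.

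**The case against.** The strongest reply is that Bonferroni is not in the written analysis at all. Read literally, Methods of Data Analysis wastes no power: a single pair at 5% has about 93%. Its weakness is the opposite one, uncontrolled error. This stands, and it is why the remedy has to begin with the analysis section.

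The order of ANOVA and pairs is also partly inferred, and the divisor is unknown. With two pairs the gain shrinks to about 7 points jointly (88.9 − 82.0) and 3.5 per contrast (92.3 − 88.8). This stands too, so the gain should be quoted with its assumptions.

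Bonferroni is valid and gives simultaneous intervals, which the closed test gives up. If only the two ketorolac contrasts matter, Holm's procedure on those two, with no omnibus step, gives 92.5% per contrast and 88.7% jointly under the equal-comparators pattern. That is essentially the same power, so the proposal is one good choice and not the only one.

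Three stronger readings are tempting and are not supported:
- A reader might infer that the trial falls short of its stated power. It does not: 81% is a per-pair figure, and three-pair Bonferroni delivers about 85%. The joint 76-77% is a different quantity, and the plan makes no claim about it. The objective is to assess efficacy and cost-effectiveness; it does not say that both pain differences must be significant.
- A reader might infer that Bonferroni can simply be deleted. Neither section makes the ANOVA binding, so deletion alone would leave about 12% family-wise error.
- A reader might infer that the proposal stops spending error on steroid against hyaluronic acid. It does not; that pair stays in the omnibus test and among the pairwise tests.

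**Conclusion.** The point holds as a cheap efficiency gain that also removes the mismatch between the sizing and analysis sections. It is not an error in the sizing. For three arms, a binding 5% omnibus test with uncorrected pairs dominates the same test followed by Bonferroni, at a family-wise error of about 5%.

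The gain is about 6-7 points per ketorolac contrast and about 12 points jointly. It assumes 25 analysed per arm, SD 2.0, ketorolac 2 points from two equal comparators, and three-pair Bonferroni as the baseline. It is about 2-3 points for the 2-point pair under means 0/1/2.

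Error control applies to one outcome at one visit. The plan has visits at 3 and 6 months and names neither as primary. Applying the rule at both would give 8.7-9.4% with all means equal, for assumed correlations of 0.7 to 0.3 between visits. The power figures also assume no loss, although Appendix A, item 3, allows removal for not completing follow-up questionnaires.

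**What to change.** In Methods of Data Analysis, and consistently in Sample Size and Justification, name one primary visit for the VAS and state:

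> Welch one-way ANOVA across the three arms at 5%; if significant, each pair is tested by Welch's t-test at 5% without further correction; if not, no pair is declared different.

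If rank tests are preferred, choose them in advance and use Kruskal-Wallis followed by Wilcoxon tests in the same way. Either choice replaces the present open option between Wilcoxon and Welch for the primary outcome. Remove the Bonferroni wording only together with this addition, and fix the text before unblinding.

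Restate the power of the Welch procedure at 25 analysed per arm as about 91-92% per ketorolac contrast and about 88% for both jointly. Name the assumed means (ketorolac 2 points from two equal comparators) and say that no loss to follow-up is assumed.

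The cost is one or two sentences of analysis wording and the restated power, with no extra patients. The downside is that the pairwise 95% intervals are not simultaneous and must be labelled so.
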